6.11.1.1 Definition of Primary Efficacy Variable

The primary efficacy variable is progression-free survival (PFS) based upon the assessment by the Investigator, defined as the time from the day of randomization to a treatment arm until documented progression or death due to any cause.

Documented disease progression includes disease progression in any compartment based on the Investigator's assessment per CTCL response criteria or documented disease progression reported during the follow-up period. The date of progression will be the earliest date at which documented disease progression can be declared.

For subjects who exhibit conditions of disease progression, but continue on the study due to a questionable clinical impression as described in Section 3.2.2.3, the subject is not considered to have progressed unless disease progression is confirmed at least 4 weeks after the date of the initial questionable disease progression. In this case, the initial date will be used as the date of disease progression.

Subjects who died without a reported prior progression will be considered to have progressed on the day of their death.

The definition of censoring date will be as follows:

- In the event that a randomized subject withdraws from the study for any reason before documented progression, the time from the day of randomization to the last post-baseline tumor assessment from any compartment (skin, blood, bone marrow, lymph node, and viscera) will be used as a censored time point.
- For subjects who are randomized to a treatment arm but have an unknown baseline assessment for a compartment, the PFS time will be censored at the randomization date if there is no post-baseline tumor assessment for that compartment or if there is any evidence of lymphoma in that compartment at post-baseline evaluation.

- For subjects randomized to a treatment arm but withdrawing prior to the first post-baseline tumor assessment for any reason other than disease progression, the PFS time will be censored at the last documented visit.
- For subjects who initiate a new anticancer therapy (including crossover to KW-0761) in the absence of a PFS event, the PFS time will be censored at the last tumor assessment (from any compartment) prior to the start of the new anticancer therapy.

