- For subjects not known to have died or have documented progression as of the end of the study, the PFS time will be censored at the date of the last post-baseline tumor assessment (from any compartment).

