6.11.2 Efficacy Analysis Methodology

6.11.2.1 Analysis of Primary Efficacy Variable

The primary comparison of progression-free survival between KW-0761 and vorinostat will be performed on the ITT set based upon the results of the on-site Investigator's assessment using a stratified Log-rank test at the one-sided 2.5% significance level. Stratification is done by disease type (MF or SS), disease stage (IB/II or III/ IV), and region (U.S., Japan, and Rest of World). A Cox proportional hazard model with treatment, disease type, disease stage, and region (U.S., Japan, and Rest of World) as covariates will be used to assess the magnitude of the treatment difference in PFS. The hazard ratio along with the 95% confidence interval obtained from the Cox proportional hazard model will be presented. Additional analyses may be performed adjusting for treatment and other baseline characteristics.

The median PFS and the 2-sided 95% confidence interval for each treatment will be estimated using the Kaplan-Meier survival analysis methods. Kaplan-Meier estimate of PFS rates and the corresponding 95% confidence interval will also be provided for each treatment arm by 6 months intervals. Plots of the Kaplan-Meier estimate of the survival distribution function over time for PFS will be presented by treatment arm.

The primary analysis of PFS will be performed when 255 total PFS events have been observed or 24 months after the last randomized subject's first dose, whichever comes first.

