6.11.2.2 Sensitivity Analyses of Primary Efficacy Variable

Three sensitivity analyses will be performed for PFS during randomized treatment period based on the on-site Investigator's assessment and the ITT Set using the following definitions:

- 1) Sensitivity Analysis 1: PFS is defined as the time from the day of randomization to a treatment arm until documented progression in any compartment based on the Investigator's assessment per CTCL response criteria or death due to any cause provided that death is not more than 8 weeks after the last post-baseline tumor assessment or the last dose of study drug (if the subject did not have any post-baseline tumor assessment).

Using this definition, the disease progression reported during the follow-up period would not be considered as an event in the sensitivity analysis, but would be a censored value on the day of the last tumor assessment.

- 2) Sensitivity Analysis 2: PFS is defined as the time from the day of randomization to a treatment arm until the earliest date of documented progression in any compartment based on the Investigator's assessment per CTCL response criteria, or clinical progression at the end of the randomized treatment, or documented disease progression reported during the follow-up period, or death due to any cause.

Using this definition, clinical progression noted at the end of the randomized treatment would be considered as an event in the sensitivity analysis.

- 3) Sensitivity Analysis 3: An additional worst-case sensitivity analysis will be performed based on the ITT Set using the following definition:

PFS is defined as the time from the day of randomization to a treatment arm until documented progression or death due to any cause. The date of documented disease progression will be the earliest date of disease progression in any compartment based on the Investigator's assessment per CTCL response criteria or disease progression reported during the follow-up period. For assessments where progression is reported by the investigator but is **not** confirmed by the IR, the progression date will be set to the last tumor assessment plus one day in the KW-0761 treatment arm and will be censored in the Vorinostat treatment arm.

The same censoring rules as described in Section 6.11.1.1 will be used for the sensitivity analyses.

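### The SAP's unknown-baseline rule censors PFS at randomization without excluding subjects who have had an event, and its place among the other rules is not stated

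*SAP*

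**What the plan says.** SAP 6.11.1.1 first defines the event: death from any cause or documented progression, where "Documented disease progression includes disease progression in any compartment". A subject who dies without reported progression counts as progressing on the day of death. Five bullets on the censoring date follow. The second covers subjects with an unknown baseline in a compartment. Their PFS is "censored at the randomization date if there is no post-baseline tumor assessment for that compartment or if there is any evidence of lymphoma" there after baseline. It has two limbs: (a) that compartment is never assessed after baseline; (b) it is assessed and shows lymphoma.

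The third bullet covers subjects "withdrawing prior to the first post-baseline tumor assessment for any reason other than disease progression" and censors them at the last documented visit. The fifth opens with "For subjects not known to have died or have documented progression as of the end of the study".

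Protocol 10.3 treats all deaths as uncensored PFS events, censors withdrawals before the first assessment at the last documented visit, and has no unknown-baseline rule. On the sensitivity analyses, SAP 6.11.2.2 says: "The same censoring rules as described in Section 6.11.1.1 will be used for the sensitivity analyses".

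**The concern.** The second bullet sits in the definition of the primary endpoint of an open-label trial with investigator-assessed PFS. It is the only one of the five that does not exclude subjects with progression or with any event. The SAP does not say whether the event definition or the bullet wins, or which bullet wins when two apply. Two programmers could therefore derive different event counts and censoring dates from the same text.

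A PFS time of zero puts the subject in no risk set of the log-rank test. Day-0 censoring thus removes the subject from a comparison that is meant to include everyone randomized. Under limb (b) the removal is triggered by a disease finding made after randomization.

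**Working it through.** **1. The bullets side by side (SAP 6.11.1.1)**

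- Bullet 1, withdrawal: limited to withdrawal before documented progression; last post-baseline assessment.
- Bullet 2, unknown baseline in a compartment: no limit; randomization date.
- Bullet 3, withdrawal before the first post-baseline assessment: progression excluded; last documented visit.
- Bullet 4, new anticancer therapy: only without a PFS event; last assessment before the therapy.
- Bullet 5, end of study: only without known death or progression; last post-baseline assessment.

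**2. Four subjects, each with an unknown baseline in one compartment**

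- Skin progression is documented; the unknown compartment is never assessed. Event definition: event. Bullet 2(a), literally: censored at day 0.
- The subject dies without reported progression after lymphoma was seen in the unknown compartment. Event definition and protocol 10.3: event. Bullet 2(b), literally: censored at day 0.
- The subject withdraws, not for progression, before any post-baseline assessment. Bullet 2(a): day 0. Bullet 3 and protocol 10.3: last documented visit. Giving events precedence does not settle this, because there is no event.
- The subject is event-free, with the other compartments followed throughout. If the unknown compartment is later clear, that follow-up is kept. If lymphoma is seen there, bullet 2(b) discards all of it.

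**3. Reproducing the plan's figure**

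Inputs from SAP 6.3: medians 169 and 254 days, one-sided 0.025, 90% power, 1:1 allocation.

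- Hazard ratio = 169/254 = 0.665; |ln| = 0.4074.
- Schoenfeld events = 4 × (1.960 + 1.282)² / 0.4074² = 253.2, rounded up to 254. The plan has 255.
- Power at 255 = Φ(0.4074 × √255 / 2 − 1.960) = Φ(1.293) = 0.902.
- Event probability with accrual A and further follow-up F: 1 − [exp(−λF) − exp(−λ(A+F))]/(λA). With A = 24 and F = 12 months it is 0.929 and 0.840, mean 0.885. Then 255/0.885 = 288, and 288 × 1.10 = 317. Both match.

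**4. Events under the SAP's trigger**

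The primary analysis "will be performed when 255 total PFS events have been observed or 24 months after the last randomized" subject's first dose. Assumptions: exponential PFS, uniform accrual, cap at 24 months after accrual ends. The share of affected subjects is assumed, because the documents give none.

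- With F = 24 the event probabilities are 0.984 and 0.941. Expected events at the cap = 158.5 × (0.984 + 0.941) = 305.1.
- With 1 / 2 / 5 / 10% of subjects set to day 0: 302.1 / 299.0 / 289.9 / 274.6. All exceed 255.
- Expected month of the 255th counted event: 30.6 without the rule; 31.0 / 31.5 / 33.1 / 36.9 with it. The delay is 0.4 / 0.9 / 2.5 / 6.3 months.
- If a further 10% contribute no event: 271.9 / 269.1 / 260.9 / 247.2. Only the last misses 255; its power is Φ(3.203 − 1.960) = 0.893.
- Simulated power when the analysis waits for 255 counted events (6,000 runs): 0.888 without the rule; 0.889 and 0.891 with 5% and 10% removed regardless of outcome.
- If the 255 were tallied before bullet 2 was applied and the lost events not replaced, losing 5% or 10% of them (13 or 26) leaves 242 or 229, with power 0.887 or 0.869.

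**5. Type I error by simulation**

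Median 169 days in both arms, unstratified log-rank, analysis at 255 counted events or the cap. Balanced case under event precedence: 20,000 runs. Other figures: average of two sets of 20,000.

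- Literal reading, every affected subject with an event set to day 0: 0.025 at 5% in each arm; 0.034 at 2% vorinostat / 8% KW-0761; 0.018 with the split reversed.
- Events take precedence, every affected subject without an event set to day 0: 0.024 when balanced; 0.016 and 0.035 for the same two splits.

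Both models are extremes, because limb (b) depends on any lymphoma in the compartment and not on the event itself. The splits are illustrative. If missing baselines fall at random, a split of 3 to 13 or worse among 16 affected subjects (5% of 317) has probability 2 × P(Bin(16, 0.5) ≤ 3) = 0.021.

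**The case against.** The strongest reply is that the section defines events first and only then opens a list of censoring dates, and a censoring date naturally applies to a censored subject. The other bullets are not drafted as a precedence scheme either: bullets 1 and 3 exclude progression but not death. This stands, and event precedence is the likelier intention. It does not settle the clash between bullets 2 and 3, and it does not change limb (b).

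Limb (b) also has a rationale. Most progression criteria are measured against baseline, and new disease counts as progression only in a compartment not previously involved (SAP 5.1.4). With an unknown baseline, lymphoma "if there is any evidence of lymphoma in that compartment at post-baseline evaluation" cannot be classed as new or pre-existing. That supports not calling progression from its mere presence. It does not require discarding follow-up in compartments that can be evaluated. The alternative has its own weakness: it credits progression-free time to someone whose status in one compartment is indeterminate. That is why it belongs in a sensitivity analysis.

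Two stronger readings are tempting:

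- A reader might infer that bone marrow counts as a compartment here, since bullet 1 includes it, so that most subjects have an unknown baseline. Protocol 7.2 and 7.2.4 and SAP 5.1 and 5.1.4 list four compartments (skin, blood, nodes, viscera). Marrow is sampled only on clinical suspicion, so that reading would censor nearly everyone and is strained.
- A reader might infer that nothing in the planned output would show the rule at work. Listing 16.2.6.16 gives each subject's randomization, progression, death and last-assessment dates beside the PFS days and censoring flag, so affected subjects can be found. What is missing is an analysis that tests the rule.

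**Conclusion.** The point holds as a defect of specification, of minor to should-fix weight. Followed literally, bullet 2 turns deaths and other-compartment progression into day-0 censoring, against the SAP's own event definition and protocol 10.3. With events taking precedence, two problems remain: conflicting dates for some early withdrawals, and loss of event-free follow-up because of a post-randomization finding. All three sensitivity analyses inherit the rule, so none measures its effect.

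The effect is likely small. Power is essentially kept if the 255 are counted as the analysis counts them, and type I error is about 0.025 when affected subjects are balanced. These figures rest on the assumed 1% to 10% affected, exponential PFS and uniform accrual.

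A reader might infer from the values between 0.016 and 0.035 that the primary test is biased. The documents do not support that. Those values need an extreme outcome-dependent removal and an unlikely imbalance together, they fall on either side of 0.025, and the number affected is unknown. No bias of known direction and no material loss of power is shown.

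**What to change.** In SAP 6.11.1.1:

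- Begin bullet 2 with: *In the absence of a PFS event (death or documented progression as defined above)*. Leave the any-compartment event definition unchanged. Restricting it to compartments with a known baseline would narrow the endpoint and could drop progression reported in follow-up.
- State that PFS events take precedence over every censoring bullet.
- State which of bullets 2 and 3 applies when both fit.
- State that lymphoma merely present in a compartment with an unknown baseline is not by itself progression.

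In SAP 6.11.2.2, add one sensitivity analysis that censors affected event-free subjects at their last post-baseline assessment of the evaluable compartments instead of day 0, and report the number affected by arm.

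The cost is SAP wording and one extra table. No new data or visits are needed.

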6.11.1.2 Definition of Key Secondary Efficacy Variables

6.11.1.2.1 Objective Response Rate

The overall response rate (ORR) is defined as the proportion of subjects who are responders (confirmed CR or PR) based on the Investigator's assessment.

Confirmed CR or PR is defined as documented CR or PR based on the Investigator's assessment of overall response per Global Composite Response Score that is subsequently confirmed by two or more consecutive observations for a minimum of 4 weeks. In the case where a subject has visit responses of CR, N/A, CR, then, as long as the time between the 2 visits of CR is greater than 4 weeks, the subject will be defined as a responder.

Subjects lacking valid data to assign a response status will be included in the denominator for response rate calculation based on the ITT Set and, hence, are considered nonresponders.

6.11.1.2.2 Changes in Skindex-29, FACT-G, and EQ-5D-3L from Baseline

The Skindex-29 is a validated instrument to measure the effect of skin disease on health-related quality of life.⁶ It is composed of 29 items assessing three domains: emotions, symptoms, and functioning. The items are scored on a 5-point Likert-type scale (never, rarely, sometimes, often, all the time). Responses to each item are transformed to a linear scale of 100 (never=0, rarely=25, sometimes=50, often=75, all the time=100) for the purpose of scale score calculation. A scale score is the mean of a subject's responses to the items in a given scale and the composite Skindex-29 score is calculated as the average of the 3 scale scores to measure the overall impact on quality of life. Higher scores indicate a higher impact of skin disease.

The FACT-G is a validated instrument for assessing health-related quality of life in subjects with cancer.⁷ The FACT-G consists of 27 items in the following 4 domains: physical

well-being (PWB), social/family well-being (SWB), emotional well-being (EWB), and functional well-being (FWB). The total FACT-G score is obtained by summing individual subscale scores. Response scores on negatively-phrased questions are reversed before summing. Higher scores for the scales and subscales indicate better quality of life.

The EuroQol/EQ-5D is a standardized, reliable and validated instrument to measure health-related quality of life. The EQ-5D self-reported questionnaire includes the EQ-5D descriptive system and a visual analog scale (VAS). The EQ-5D 3 level version (EQ-5D-3L) descriptive system comprises the following dimensions: mobility, self-care, usual activities, pain/discomfort and anxiety/depression. Each dimension has 3 levels: no problems, some problems, extreme problems. The EQ-5D index score is calculated based on the descriptive system using a set of item weights (value sets) to derive a single score ranging from -0.109 to 1, with 1 representing full health. The value sets for the US will be used for the calculation of the EQ-5D index score.⁸ The EQ-5D self-reported questionnaire also includes a visual analog scale (VAS), which records the respondent's self-rated health status on a graduated (0-100) scale, with 100 = best imaginable health state and 0 = worst imaginable health state.

Skindex-29, FACT-G, and EQ-5D-3L will be evaluated at baseline (Cycle 1 Day 1), end of Cycle 1, then every 8 weeks (i.e., end of Cycle 3, 5, etc), and at the End of Treatment Visit. Measurements at end of cycle 1 are defined as the latest value obtained from Cycle 1 Day 26-28 or Cycle 2 Day 1. Measurements at the end of Cycle x, where x = 3, 5, 7, ..., etc, are defined as the latest value obtained from Cycle x Day 26-28, Cycle x Q8 weeks, or Cycle (x+1) Day 1.

The improvement (change from baseline) for each of the quality of life measurements described above will be evaluated at each timepoint as specified in the study procedure tables for each arm.

Missing data for Skindex-29 and FACT-G will be handled according to the questionnaires' scoring guidelines. For Skindex-29, if responses to more than 25% of items are missing overall, the Skindex-29 score will be treated as missing. If any scale has more than 25% of the responses missing, the scale score is missing. The scale scores are the average of the non-missing items in a given scale. For FACT-G, if more than 50% of the items are responded for a subscale, the subscale scores will be prorated by multiplying the sum of the subscale by the number of items in the subscale and then dividing by the number of items actually responded. The total FACT-G score will be scored only if the overall item response rate is greater than 80%. For EQ-5D-3L, the EQ-5D index score will be treated as missing if not all five descriptors are responded.

6.11.1.3 Definition of Other Secondary Efficacy Variables

6.11.1.3.1 Best Overall Response

Best overall response is defined as the best response recorded across all timepoints from the start of treatment until disease progression/recurrence or end of treatment. The subject's best response assignment will depend on the achievement of both measurement and confirmation criteria.

6.11.1.3.2 Duration of Response and Time to Response

Duration of response (DOR) is defined as the time from the date criteria are met for CR/PR (whichever is first recorded) until the first date that PD or death is objectively documented. Subjects who do not relapse will be censored at the day of their last tumor assessment (from any compartment).

Time to response (TTR) is defined as the time from the date of randomization to the date criteria are first met for CR/PR (whichever is first recorded). Subjects who do not respond over the course of the study will have a missing value for TTR.

6.11.1.3.3 Changes in Pruritus Evaluation

Pruritus Evaluation includes the Likert Scale and the Itchy QoL. The Likert scale for pruritus evaluation uses a numbered scale from 0 to 10 to measure the level of itching for pruritus with 10 indicating worst itch imaginable and 0 indicating no itch. The Itchy QoL is a validated pruritus-specific quality of life instrument.⁹ It includes 22 pruritus-specific questions covering three major domains: symptoms, functioning, and emotions. The subscale scores consist of the average of the responses to the items in a given subscale. The overall score is the average of the responses to all items. Higher Itchy QoL scores indicate worse quality of life. Missing data in Itchy QoL questionnaire will be handled according to the following rule: if responses to more than 25% of items are missing overall, the overall score will be treated as missing; if any scale has more than 25% of the responses missing, the scale score is missing.

Pruritus Evaluation will be performed at each timepoint specified in the study procedure tables for each arm.

6.11.1.4 Definition of Exploratory Efficacy Variables

6.11.1.4.1 Overall Survival (OS)

Overall survival is defined as the time from the date of randomization until the date of death of the subject due to any cause. Subjects who are still alive at the end of the survival

follow-up period or are lost to follow-up at the time of analysis will be censored on the last date the subject is known to be alive.

6.11.1.4.2 Time to Treatment Failure (TTF)

Time to treatment failure is defined as the time from the day of randomization to a treatment arm until discontinuation of randomized treatment due to any reason except for those subjects who discontinued randomized treatment due to one year on treatment with a CR.

Subjects who experienced an overall CR and discontinued randomized treatment after one year of treatment will be censored at the last dose date of the randomized treatment. Subjects who were randomized but did not take any study drug will be censored at the last documented visit date.

